In spite of existing work studying rTMS as a treatment modality in schizophrenia, there are no studies that have examined the effects of precuneus directed rTMS on either EM deficits or the neurocircuitry subserving EM in schizophrenia. It is also important to note that the vast majority of studies using rTMS in schizophrenia have examined chronic populations where confounds associated with prolonged duration of illness may be present. EPP is a desirable population to study because these individuals tend to have fewer psychiatric and physical comorbidities and less antipsychotic drug exposure, all of which are factors that may confound investigations of new treatment interventions for this illness. In light of the significant unmet medical need associated with schizophrenia and the grave clinical effect of disrupted EM in the illness, rTMS modulating the precuneus, and potentially EM circuitry, represents an unexplored and potentially novel potential treatment option.

This study proposes to combine functional magnetic resonance imaging (fMRI) with inhibitory LF (1 Hz) and excitatory HF (20 Hz) rTMS protocols to interrogate the effects of rTMS targeting the precuneus on: 1) precuneus activation during EM task performance; 2) functional connectivity between the precuneus and key EM circuitry, specifically the DLPFC, ACC, and hippocampus and 3) performance during an in-scanner scene encoding and recognition EM task. This study will provide vital preliminary data on target engagement informing future clinical trials seeking to utilize rTMS to treat EM impairment in schizophrenia. This is an important population for study because if effective, rTMS may represent a novel treatment for EM deficits in schizophrenia. This study will also seek to refine the understanding of the brain circuitry that mediates the potential pro-EM effects of rTMS through the use of fMRI at baseline and following the course of rTMS administration.

[figure not shown]

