## 2.0 Specific Aims and Hypothesis

The **first primary aim** is to demonstrate how targeting the precuneus with rTMS impacts functional activation (FA) in individuals with schizophrenia during EM tasks. We predict that, compared to sham stimulation, 1 Hz rTMS will result in decreased FA of the precuneus and 20 Hz rTMS will result in increased FA of the precuneus. The **second primary aim** is to demonstrate how targeting the precuneus with rTMS impacts precuneus functional connectivity (FC) in individuals with schizophrenia. We predict that compared to sham stimulation, FC between the precuneus, the DLPFC, the hippocampus, and the ACC will be decreased in response to 1 Hz rTMS and increased in response to 20 Hz rTMS. The **third primary aim** is to characterize the relationships between EM performance and changes in precuneus functional activation and connectivity. We predict that improved EM performance will be associated with increased precuneus functional activation and connectivity, while poorer EM performance will be associated with decreased precuneus functional activation and connectivity. The **secondary aim** is to characterize how targeting the precuneus with rTMS affects episodic memory performance in individuals with schizophrenia. We predict that compared to sham stimulation, 1 Hz rTMS will impair EM performance and that 20 Hz rTMS will improve EM performance.

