## **13.0 Statistical Considerations**

### **Analyses**

#### *Power Analyses*

In terms of the power to detect a significant effect of precuneus directed rTMS on EM performance or neurocircuitry, there are no known calculations with EPP patients. We plan to enroll 30 subjects and anticipate a 20% drop out rate, thus yielding 24 completers. This is consistent with our previous clinical trial efforts in early phase psychosis populations, including a study of adjunct rTMS for cognitive impairment and negative symptoms. For all planned analyses, a total of 24 subjects in a cross-over design will result in 0.8 power to detect an assumed treatment difference at medium effect size 0.6; using an alpha level of 0.05 and conservatively assumed a within-subject correlation of 0.5. As no previous precuneus rTMS pilot study was available, this standardized effect size of 0.6 is considered to a conservative estimate to detect the significant results.

[figure not shown]

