#### *Statistical Analyses*

[figure not shown]
Intent-to-treat (ITT) analysis will be conducted, and thus all randomized subjects will be included. ITT is the most conservative approach for detecting a treatment effect, because the inclusion of subjects who do not complete the intervention will serve to underestimate rather than overestimate any treatment effect. Sensitivity analyses including a subset analysis using a “completers only” analysis will be performed to test the robustness of the findings. Statistical tests will be performed based on two-sided test at the 5% level of significance.

Descriptive characteristics at baseline will be summarized for the whole sample. For continuous variables, the mean and standard deviation will be presented. For categorical variables, the number and percent will be reported.

Primary analyses: For each subject, change scores in activation of the precuneus (aim 1), functional connectivity (aim 2), and EM performance (aim 3) will be calculated at each treatment by using (post - baseline). We will employ a mixed model for repeated measures ANCOVA, of the general form for each measure:  $change_{ijk} = \mu + \alpha_i + b_{ij} + \gamma_k + \beta X_{ijk} + \tau_d(i, k) + e_{ijk}$ , where  $\mu$  is overall mean;  $\alpha_i$  is the effect of the  $i$ th treatment sequence ( $i = 1, 2, \dots, 6$ );  $b_{ij}$  is the random effect with variance  $\sigma_b^2$  for the  $j$ th subject ( $j = 1, 2, \dots, 24$ ) of the  $i$ th treatment sequence;  $\gamma_k$  is the period effect ( $k = 1, 2, 3$ );  $\beta X$  is the baseline value;  $\tau_d(i, k)$  is the direct effect of the treatment administered in period  $k$  of sequence group  $i$ ; and  $e_{ijk}$  is the random error with variance  $\sigma^2$  for the subject in period  $k$ . Based on this model, we will compare the treatment difference in change score between 1 Hz and Sham as well as 20 Hz and Sham. Under the assumption of missing at random, this mixed effect model will provide the unbiased estimates.

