**Brain Imaging Analyses:** **Aim 1.** Data analysis of the blood-oxygen level-dependent (BOLD) time series will utilize standard preprocessing through the AFNI software package. Standard preprocessing includes motion correction, despiking, detrending, smoothing, and exclusion of signal and motion outlier time points. Each condition's timing will be convolved with a hemodynamic response function to model an ideal response for that condition. General linear modeling will provide a regression coefficient estimate (beta) of the BOLD response to each condition (Target correct; Foil correct; Target incorrect; Foil incorrect). We will also include regressors of no interest for motion and motion derivatives to reduce noise. For our primary analysis, we will create a region of interest (ROI) as a 10-mm radius sphere around our rTMS target in the precuneus. **fMRI Contrast:** Each event type will be modeled separately. Brain activity will be examined by contrasting the estimated beta coefficients for correct trials only (Target correct vs. Foil correct). We will **extract the mean response from this contrast from our precuneus ROI** and evaluate the aim via a mixed model for repeated measures. **Aim 2.** Beyond standard preprocessing, time-series data will be filtered to extract low frequency (< 0.08 hz) BOLD data. The ANATICOR approach (within AFNI) will be used to reduce noise from physiological or hardware sources. ANATICOR utilizes tissue segmentation to control for spatially coherent fluctuations emanating from non-gray matter. Structural regions of interest (ROIs) will be defined on each side with Talairach-based atlases available via AFNI software for the ACC and bilateral middle frontal gyrus, in addition to the spherical precuneus ROI. Visual inspection of ROIs will ensure their correct position. The mean preprocessed time series will be extracted from each ROI, and time-series correlations between ROIs will be calculated. These correlations will be used as the dependent variable in a mixed model for repeated measures ANCOVA, with post-hoc tests as necessary. Supplementary analyses will examine connectivity differences of the precuneus ROI across the entire brain (corrected  $p < .05$ ).

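### The second primary aim predicts a change in precuneus–hippocampus connectivity, but the Aim 2 region list omits the hippocampus, so that connection has no primary ROI-level test

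*Combined protocol and SAP*

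**What the plan says.** Section 2.0 states, under the second primary aim, that "FC between the precuneus, the DLPFC, the hippocampus, and the ACC will be decreased in response to 1 Hz rTMS", and predicts the opposite direction for 20 Hz. Section 1.0 lists the same targets among the study's objectives: "functional connectivity between the precuneus and key EM circuitry, specifically the DLPFC, ACC, and hippocampus".

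The analysis is set out in section 13.0.

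- Under Brain Imaging Analyses, Aim 2, the regions are specified "with Talairach-based atlases available via AFNI software for the ACC and bilateral middle frontal gyrus, in addition to the spherical precuneus ROI". On laterality, the text states: "Structural regions of interest (ROIs) will be defined on each side". A mean time series is taken from each of these regions and correlated with the others. Then: "These correlations will be used as the dependent variable in a mixed model for repeated measures ANCOVA".
- The same paragraph ends with a fallback: "Supplementary analyses will examine connectivity differences of the precuneus ROI across the entire brain", at a corrected threshold of p < .05.
- Under Statistical Analyses, the primary model is applied to activation, functional connectivity and EM performance. For each measure, "we will compare the treatment difference in change score between 1 Hz and Sham as well as 20 Hz and Sham". No brain regions are named there.
- Under Power Analyses: "For all planned analyses, a total of 24 subjects in a cross-over design will result in 0.8 power to detect" a standardized difference of 0.6.

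**The concern.** The aim names three partner regions for the precuneus. The analysis supplies two: the ACC, and the middle frontal gyrus, which apparently stands for the DLPFC although the text does not say so. A statistician following section 13.0 to the letter would finish the primary Aim 2 analysis with no precuneus–hippocampus estimate, although part of a primary prediction depends on it.

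If the gap is noticed only after the data have been seen, the choice of hippocampal atlas label, boundary and side would be made with results in view. The gap also carries forward. The third primary aim relates EM performance to connectivity change, and the first mediation analysis takes connectivity as its outcome. Neither says which connections count.

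**Working it through.** **The plan's own figure.** Inputs from Power Analyses and Statistical Analyses: 24 completers, effect size 0.6, within-subject correlation 0.5, two-sided alpha 0.05. Treating each sham contrast as a paired comparison:

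- dz = 0.6 / √(2 × (1 − 0.5)) = 0.6
- n = 24, df = 23, noncentral t: power = 0.804, against 0.8 stated
- Enrolment: 24 / (1 − 0.20) = 30, as stated

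The paired t-test approximates the planned mixed model; with about 44 residual df the power is 0.820. The stated figure reproduces. It describes any single contrast in this trial and does not measure the omission. It matters here only because adding a region does not alter it.

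**Connections predicted against connections defined.**

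| Partner of the precuneus | Aim (2.0, 1.0) | Region list (13.0, Aim 2) |
|---|---|---|
| DLPFC | yes | middle frontal gyrus, apparently |
| ACC | yes | yes |
| Hippocampus | yes | no |

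Missing: 1 of 3. Section 1.0 supports this count, because it describes connectivity between the precuneus and three other structures. The sentence in section 2.0 can also be read as all pairs among four regions. That gives 4 × 3 / 2 = 6 pairs, of which the 3 involving the hippocampus are missing.

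**Contrasts left without a primary ROI-level test** (precuneus-to-region reading):

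- Sides combined: 1 connection × 2 sham contrasts = 2
- Sides separate: 1 × 2 sides × 2 = 4

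The plan defines regions on each side but does not say how sides enter the model, so both counts are given.

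**Effect of adding the region on the Aim 2 test family.**

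- Sides combined, now: 2 connections × 2 contrasts = 4. Chance of at least one false positive = 1 − 0.95⁴ = 0.185
- Sides combined, after: 3 × 2 = 6. Chance = 1 − 0.95⁶ = 0.265
- All regions split by side: 8 rising to 12. Chance = 1 − 0.95⁸ = 0.337 rising to 1 − 0.95¹² = 0.460

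These figures assume independent, unadjusted tests at 0.05. Contrasts sharing a sham arm and a precuneus region will be correlated, so they indicate scale only. The plan gives no multiplicity rule for the ROI contrasts. Purely for illustration, a Bonferroni split within Aim 2 would put power per contrast at 0.596 with 4 tests and 0.532 with 6.

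**Scans involved.** One baseline and three post-stimulation scans per subject make 4. The ITT analysis includes all randomized subjects, so at most 4 × 30 = 120 scans; 24 completers give 4 × 24 = 96.

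**The case against.** The strongest reply is that the hippocampus is not left out altogether. The supplementary whole-brain analysis starts from the same precuneus region, uses a stated corrected threshold and covers the hippocampus. The primary model, baseline covariate, sham contrasts and significance level are also fixed for functional connectivity in general. This stands to the extent that a reader might infer that the plan contains no pre-specified analysis that could detect a hippocampal change; the documents do not support that reading. But the whole-brain analysis is labelled supplementary, does not name the hippocampus and tests it only within a search of the entire brain. It does not stand in for a primary test of a primary prediction.

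A second reply is that late selection is partly constrained. The plan fixes the atlas family, bilateral definition and visual checking for the other structural regions, and a repair would probably follow suit. That is reasonable, but nothing in the text binds a hippocampal region to it.

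A third is that this is a single-site pilot meant to yield preliminary data, and that the omission looks like a drafting slip. That bears on severity, not on whether the mismatch exists. The region list is a complete sentence with no sign that it is illustrative.

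**Conclusion.** The concern holds as an aim–analysis mismatch that should be fixed. There is no primary ROI-level test of precuneus–hippocampus connectivity: 1 of 3 precuneus-to-region connections, or 3 of 6 pairs on the broader reading. On the narrower reading, this leaves 2 predicted sham contrasts with sides combined or 4 with sides separate.

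The conclusion rests on two assumptions: that the middle frontal gyrus represents the DLPFC, and that no hippocampal region is defined in a figure not available for this review. The readable text defines none.

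A reader might go further and infer that the sample size or power statement is wrong, or that the analyses of the ACC and middle frontal gyrus are compromised. Neither follows. The stated power reproduces, it concerns analyses that are planned, and the listed connections are unaffected.

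**What to change.** Do one of the following before the data are analysed.

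1. **Add the region.** Put the hippocampus on the Aim 2 list, from the same AFNI Talairach-based atlas source. State how left and right are combined. Analyse its correlation with the precuneus in the same mixed model, with the same 1 Hz–sham and 20 Hz–sham contrasts. It would help to state at the same time that the middle frontal gyrus is the DLPFC region. The cost is a short edit, one more extraction from scans already planned (up to 120), and the larger test family shown above, which the plan should acknowledge. Sample size and unadjusted power per contrast do not change.

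2. **Narrow the aim.** Label the hippocampal connection exploratory in section 2.0, make section 1.0 consistent, and state which connections the third primary aim and the mediation analysis cover. The cost is a few text edits and a narrower primary claim.

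Neither option needs new visits, scans or patients.

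### Aim 2 puts several between-region correlations into a model written for one value per session, without saying which enter, how they are combined, or how error is controlled

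*Combined protocol and SAP*

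**What the plan says.** Section 2.0 makes precuneus connectivity the second primary aim and predicts one direction for all targets: "FC between the precuneus, the DLPFC, the hippocampus, and the ACC will be decreased in response to 1 Hz rTMS", with the opposite change under 20 Hz.

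The Aim 2 text in Section 13.0 (Brain Imaging Analyses) says that structural regions "will be defined on each side with Talairach-based atlases available via AFNI software for the ACC and bilateral middle frontal gyrus", and adds the spherical precuneus region. It then calculates correlations between regions, without limiting them to pairs that include the precuneus, and states: "These correlations will be used as the dependent variable in a mixed model for repeated measures ANCOVA, with post-hoc tests as necessary".

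The only model is under Statistical Analyses, offered as a form to be applied measure by measure. Its indices are sequence, subject and period. It has a random subject intercept and an error term that "is the random error with variance" σ², one per subject and period. Two contrasts are drawn from it: 1 Hz against sham and 20 Hz against sham. On the level, the plan says: "Statistical tests will be performed based on two-sided test at the 5% level of significance". No adjustment is given for the Aim 2 correlations; only the supplementary whole-brain analysis is described as corrected.

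**The concern.** The model accepts one number per session and Aim 2 supplies several. Aim 1 does not have this problem, because it extracts one mean response from one region.

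An analyst following the text has to choose among separate models, a stacked model and an average, and among precuneus pairs and all pairs. These choices lead to different error rates and different power, and nothing stops them from being made after the results are seen. The mediation analysis depends on the same choice: its first step needs a significant treatment effect on change in connectivity, treated as a single variable.

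**Working it through.** **1. The plan's own figure.** Power Analyses states that 24 completers "will result in 0.8 power to detect an assumed treatment difference at medium effect size 0.6; using an alpha level of 0.05". The correlation between a subject's measurements is taken to be 0.5. For a paired comparison, dz = 0.6/√(2(1 − 0.5)) = 0.6. With n = 24 and two-sided 5%, the noncentral t gives 0.804 on 23 df, or 0.820 on about 44 df for the three-period model. The stated 0.8 reproduces, for one contrast on one measure. Dropout also agrees: 30 × 0.80 = 24.

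**2. Counts.** k regions give k(k − 1)/2 pairs, of which k − 1 include the precuneus.

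| Reading | Regions | Pairs | With precuneus |
|---|---|---|---|
| ACC as one midline region | 4 | 6 | 3 |
| ACC and middle frontal gyrus, left and right, plus precuneus | 5 | 10 | 4 |
| As above plus left and right hippocampus | 7 | 21 | 6 |

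The second row fits the wording best and is used below.

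**3. One model per precuneus pair.** This gives 4 pairs × 2 contrasts = 8 tests, each at 5%. If all 8 were independent, the chance of any false positive would be 1 − 0.95⁸ = 0.337. The two contrasts share the sham session, and the pairs are correlated. Simulated under the null (24 subjects, 3 sessions), with between-pair correlation r assumed:

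| r | 0 | 0.3 | 0.5 | 0.7 | 0.9 |
|---|---|---|---|---|---|
| Any false positive among 8 | 0.312 | 0.298 | 0.270 | 0.232 | 0.165 |

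A separate simulation put the upper end at 0.32, so the range is about 17% to 32%. Bonferroni over the 8 tests (0.00625 each) would leave power of 0.49 to 0.53 per test at effect 0.6.

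**4. The 4 pairs stacked, subject intercept only.** Set the session-level variance to 1. Let r be the correlation between pairs within a session, and ω² the stable subject variance specific to a pair. The true variance of a contrast is 2(1 + 3r)/(24 × 4). The model uses 2s²/(24 × 4), where approximately

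s² = [2(1 + 3r) + 9(1 − r) + 9ω²]/11,

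so the actual error is about P(|Z| > 1.96·√(s²/(1 + 3r))). Correlation within a session raises the true variance. Pair-specific stable variance inflates s² and works the other way.

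A plausible r comes from the formula for two sample correlations, a and b, that share a variable, with c the correlation between the other two: [c(1 − a² − b²) − ½ab(1 − a² − b² − c²)]/[(1 − a²)(1 − b²)]. Assume a = b = 0.3. With c = 0.7 (left-right) it gives 0.68; with c = 0.4 (ACC with middle frontal gyrus) it gives 0.36. The average over the 6 combinations is (2 × 0.68 + 4 × 0.36)/6 = 0.47.

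- r = 0.47, ω² = 0: s² = (4.82 + 4.77)/11 = 0.872; 1.96 × √(0.872/2.41) = 1.18; error 0.24.
- r = 0.47, ω² = 1: s² = (4.82 + 4.77 + 9)/11 = 1.690; 1.96 × √(1.690/2.41) = 1.64; error 0.10.
- r = 0, ω² = 1: s² = 20/11 = 1.818; 1.96 × √1.818 = 2.64; error 0.008.

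Simulation at r = 0.47 gives about 11% to 23% (24% at the top in a repeat run). Simulated error per contrast at other values, with stable variance equal to session variance:

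| Stable variance specific to the pair | r = 0 | 0.1 | 0.2 | 0.3 | 0.5 |
|---|---|---|---|---|---|
| None | 0.048 | 0.086 | 0.132 | 0.169 | 0.262 |
| Half | 0.022 | 0.045 | 0.078 | 0.105 | 0.159 |
| All | 0.008 | 0.022 | 0.044 | 0.068 | 0.111 |

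**5. One averaged precuneus value per session.** The error is 5% per contrast and about 9% over both. If each of the 4 pairs has effect 0.6, the average has dz = 0.6/√((1 + 3r)/4): 0.87, 0.77 and 0.72 at r = 0.3, 0.47 and 0.6, with power 0.98, 0.95 and 0.92. If only the two pairs of one target respond, dz at r = 0.47 halves to 0.39 and power falls to about 0.44.

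**The case against.** A reader might infer that Aim 2 fails its 5% level however it is read. The documents do not support that. The 5% is stated for individual tests and no family-wise level is claimed. The model is offered measure by measure, so fitting it once per connection is a fair reading, and every test then keeps 5%. In the stacked case, the inflation depends on correlations and variance components that the documents do not give, and part of the plausible range lies at or below 5%. Averaging to one value per session is also open and fits the printed model.

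Nor should the two sets of rates be merged into one multiplier of 5%. The stacked figures are per contrast; the separate-model figures are for any of 8 tests. The fair comparator for the latter is the composite's 9% over both contrasts, not its 5% for one.

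It is also tempting to say that all 10 correlations will be tested. Section 2.0 and the MRI procedures in Section 6.0 speak of connectivity with the precuneus, which points to the 4 pairs. The Aim 2 text does not make that restriction, so it should be written in.

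Finally, this is a single-site pilot, and a composite cannot show which connection changed. That lowers the urgency and is a reason to keep target-specific results. It does not supply the missing rule.

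**Conclusion.** The gap is real and should be fixed. A primary aim has several candidate outcomes per session, a model for one, and no rule for selecting, combining or adjusting. The counts of 10 and 4 rest on the five-region reading. The sizes in steps 3 and 4 rest on 24 completers and assumed dependence between pairs. What holds throughout is narrower: separate tests raise the chance of some false Aim 2 finding well above the 9% that two contrasts on a single outcome would carry, and stacking without further random terms may breach 5% per contrast. Neither shows that the plan breaks a level it states. The claim of 0.8 power for all planned analyses is reproduced only for one contrast on one measure at an unadjusted 5%.

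**What to change.** Before the composite is fixed, reconcile the Aim 2 region list with Section 2.0, which names the hippocampus as a target; the Aim 2 list leaves it out. Then replace the sentence on the dependent variable with wording such as:

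*The Aim 2 primary outcome is one value per session: the mean connectivity between the precuneus sphere and its target regions, left and right averaged. It is analysed with the stated model for 1 Hz against sham and 20 Hz against sham. Target-specific values, left and right averaged, are secondary and Holm-adjusted. Correlations that do not involve the precuneus are descriptive.*

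For the two contrasts, either state that the error is 5% each and about 9% over both, or apply Holm across the two. At its first step (0.025), power for a single measure at effect 0.6 is 0.70 on 23 df.

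If a stacked model is preferred, restrict it to precuneus pairs and add a connection factor, a subject-by-session random effect and a subject-by-connection random effect.

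The cost is wording only; no new data are needed, although an added hippocampus region would have to be extracted from the existing scans. The downside is dilution when only one target responds, which is why the target-specific tests are kept.
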